5.8.1. Adverse Events

In general, the primary focus of AE reporting will be on TEAEs summarized in respective TEAE periods, specifically the Part A, Part B, Part C, and pooled treatment periods.

If an AE onset date (occurrence, worsening, or becoming serious) is incomplete, an imputation algorithm will be used to classify the AE as pre-treatment, treatment-emergent, or post-treatment. The algorithm for imputing date of onset will be conservative and will classify an AE as treatment-emergent unless there is definitive information to determine pre-treatment or post-treatment status. Details on classification of AEs with missing or partial onset dates are provided in [Section 6.3](#).

Adverse event incidence tables will present the number (n) and percentage (%) of patients experiencing an AE by SOC and PT. In addition, incidence tables by SOC, HLG, HLT, and PT will be provided for all TEAEs, serious TEAEs, and TEAE leading to permanent treatment discontinuation. Multiple occurrences of the same event in the same patient will be counted only once in a table. For tables presenting severity of events, the worst severity will be chosen for patients with multiple instances of the same event. The denominator for computation of percentages is the respective safety analysis set.

AE incidence tables will present data by SOC sorted alphabetically and PT sorted by decreasing frequency and summarize the number (n) and percentage (%) of patients experiencing an AE.

Analysis of all treatment-emergent adverse events

The following TEAE summaries will be generated:

- Overview of TEAEs, summarizing number (%) of patients with any
 - TEAE;
 - Serious TEAE;
 - TEAE leading to death;
 - TEAE leading to permanent treatment discontinuation.
- All TEAEs by primary SOC, HLGT, HLT, and PT
- All TEAEs by primary SOC and PT
- Number (%) of patients experiencing common TEAE(s) presented by primary SOC and PT (PT incidence ≥ 2 patients)
- All TEAEs relationship (related/not related) to evinacumab
- All TEAEs by maximum severity (i.e., mild, moderate or severe)
- A common TEAE related to any clinically significant signal will be further characterized as appropriate. The characterization of the clinically significant signal can include Kaplan-Meier curves for time from first dose to first occurrence of selected TEAE, time to resolution, and event duration. Patients without any event will be censored at the end of the respective TEAE period.

Analysis of all treatment emergent serious adverse event(s)

- All Serious TEAEs by primary SOC, HLGT, HLT, and PT
- All Serious TEAEs by primary SOC and PT
- Patient listings of serious TEAEs will be provided in the report appendix
- All Serious TEAEs relationship (related/not related) to evinacumab
- A serious TEAE related to any clinically significant signal will be further characterized as appropriate. The characterization of the clinically significant signal can include Kaplan-Meier curves for time from first dose to first occurrence of selected TEAE, time to resolution, and event duration. Patients without any event will be censored at the end of the respective TEAE period.

Analysis of all treatment-emergent adverse event(s) leading to treatment discontinuation

- All TEAEs leading to permanent treatment discontinuation, by primary SOC, HLGT, HLT, and PT
- All TEAEs leading to permanent treatment discontinuation, by primary SOC and PT
- Patient listings of TEAEs leading to permanent treatment discontinuation will be provided in the report appendix.

- A TEAE leading to permanent treatment discontinuation and related to any clinically significant signal will be further characterized as appropriate. The characterization of the clinically significant signal can include Kaplan-Meier curves for time from first dose to first occurrence of selected TEAE, time to resolution, and event duration. Patients without any event will be censored at the end of the respective TEAE period.

Patient Deaths

The following summaries of deaths will be generated.

- Number (%) of patients who died by study period (TEAE and post-treatment) and reason for death;
- TEAEs leading to death (death as an outcome on the AE CRF page, as reported by the Investigator) by SOC and PT.

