14. At weeks 8 and 16 of the follow-up period all patients will be contacted by phone to query LMT compliance, to inquire about AEs or changes to concomitant medications, confirm required contraception use, and remind patients of pregnancy reporting. Sexually active females of childbearing potential will report the results of their home pregnancy test. For patients who decide to enter a compassionate use or early access program, the EOT visit will be their last visit and they will forgo the 24-week follow-up period.
15. Overlapping assessments completed at the EOT visit of Part A or Part B do not need to be duplicated during visit 1 of Part C. Part C visit 1 should occur on the same day as Part A visit 11 or Part B visit 11. All necessary assessments are listed in the applicable SOE (Part A or Part B) column for visit 11.
16. Patient can only receive the dose once all assessments from Part A or Part B Visit 11 are completed.
17. For patients who decide to enter a CUP or EAP, the EOT visit will be their last visit and they will forgo the 24-week follow-up period.

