1.2.4. Modifications from the Statistical Section in the Final Protocol

The content of this SAP reflects the content of the statistical section of Protocol R1500-CL-17100 Amendment 1.

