- The total number of patients who completed Part B treatment period as collected on the End of Treatment e-CRF.

- The total number of patients who completed Part B treatment period, defined as at least 20 weeks of study treatment administration and visit week 24 performed.
- The total number of patients who prematurely discontinued Part B treatment, and the reasons for discontinuation collected on the End of Treatment e-CRF
- The total number of patients in Part B who do not proceed into Part C and complete the last study follow-up visit (i.e. Follow-up Week 20).
- The total number of patients in Part B who do not proceed into Part C and do not complete the study follow-up period, defined as the last visit performed less than 22 weeks after the last study treatment administration. Patients who died during the study are excluded.

Patient milestone categories for Part C are defined below. As applicable, percentages will be calculated using a denominator of the number of patients receiving Part C study treatment.

- The total number of patients receiving Part C study treatment.
- The total number of patients ongoing in Part C (applicable for the first step and second step analyses)
- The total number of patients who completed Part C treatment period as collected on the End of Treatment e-CRF.
- The total number of patients who completed Part C treatment period, defined as at least 44 weeks of Part C study treatment administration and Part C visit week 48 performed.
- The total number of patients who prematurely discontinued study treatment during Part C, and the reasons for discontinuation collected on the End of Treatment e-CRF.
- The total number of patients in Part C who complete the last study follow-up visit (i.e. Follow-up week 24).
- The total number of patients who did not complete the study follow-up period, defined as the last visit performed less than 22 weeks after the last study treatment administration. Patients who died during the study are excluded.

The following patient populations for analyses are defined in Section 4.2:

- Efficacy populations (for Part B only): ITT and mITT populations
- Safety analysis set
- Part C safety analysis set
- Pooled safety analysis set
- Anti-evincumab antibody (ADA) analysis set
- Neutralizing anti-evincumab antibody (NAb) analysis set
- Pharmacokinetic (PK) analysis set
- Target analysis set

- Concentration-Response (C-R) analysis set

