4.8.1. Adverse Events Variables

The period of safety observation starts from the time when the patient gives informed consent and continues into the following periods:

- The PRE-TREATMENT period is defined from the day the ICF is signed to the day before the first dose of study treatment administration.
- The treatment-emergent adverse event (TEAE) period (Part A or Part B) is defined from the day of the first dose of study treatment administration to the day of the last dose of study treatment administration in Part A or Part B respectively + 168 days (24 weeks). For patients entering Part C, the TEAE period is truncated at the day before the first study treatment administration in Part C.
- The Part C TEAE period is defined from the day of the first study treatment administration in Part C to the day of the last study treatment administration in Part C + 168 days (24 weeks).
- The pooled TEAE period is defined below:
 - Part A Patients: defined as the Part C TEAE period.
 - Part B Patients: defined from the day of the first study treatment administration in Part B to the day of the last study treatment administration in Part C + 168 days (24 weeks) or to the last study treatment administration in Part B + 168 days (24 weeks) for patients not entering into Part C.
- The POST-TREATMENT period is defined from the day after the end of the respective TEAE periods to the last study visit.

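### Event-free patients who leave for compassionate use or early access stay in the Kaplan-Meier risk set for 20 to 24 unobserved weeks, and their permitted exit is counted as incomplete follow-up

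*SAP*

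**What the plan says.** **Curves and censoring (SAP 5.8.1).** If a TEAE relates to a clinically significant signal, "The characterization of the clinically significant signal can include Kaplan-Meier curves for time from first dose to first occurrence of selected TEAE". The rule for the others is: "Patients without any event will be censored at the end of the respective TEAE period". It appears three times: for common TEAEs, for serious TEAEs, and for TEAEs leading to permanent discontinuation.

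**End of the TEAE period (SAP 4.8.1).** For Part C, and for the pooled period of patients who enter Part C, it is the last Part C dose plus 168 days. Two truncations exist. One concerns the Part A or Part B period: "For patients entering Part C, the TEAE period is truncated at the day before the first study treatment administration in Part C". The other, in SAP 7.4, ends the period at the data cut-off for ongoing patients, at the first and second analysis steps only. Nothing truncates at last contact in the final analysis.

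**Exit at EOT (current protocol).** Footnote 17 to the Part C schedule (Section 9.1.1.3) says: "For patients who decide to enter a CUP or EAP, the EOT visit will be their last visit". Sections 6.1, 9.1 and 9.1.2 give the same waiver, and Section 10.1.2 applies it to the 24 weeks of post-dose adverse event collection.

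**Disposition (SAP 4.5).** Part C patients who did not complete follow-up are "defined as the last visit performed less than 22 weeks after the last study treatment administration". Only deaths are excluded.

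**Version (SAP 1.2.4).** "The content of this SAP reflects the content of the statistical section of Protocol R1500-CL-17100 Amendment 1". The CUP/EAP waiver came with Amendment 2, and the SAP does not mention these programmes.

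**The concern.** Censoring should stop a patient's contribution when observation stops. Here the censoring date is calculated from the last dose, whether or not anyone saw the patient up to that date. A patient who goes from the EOT visit into a CUP or EAP, and may still be receiving evinacumab there, is carried as at risk and event-free through months in which the study makes no visits or calls. Those patients enlarge the denominator for any later event, so the estimated late incidence is too low. The error runs in the reassuring direction, in the part of the study meant to describe long-term safety in children.

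The disposition table has a related gap. A patient who used an exit that the protocol allows and a patient who was lost fall into the same row.

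**Working it through.** **Inputs.** Part C week 44 is day 309 and week 48 (EOT) is day 337 (SAP Table 4). The TEAE period ends at last dose + 168 days (SAP 4.8.1). The non-completion threshold is 22 weeks = 22 × 7 = 154 days (SAP 4.5). Planned numbers are 6 in Part A and 14 in Part B, 20 in all (protocol 11.2).

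**1. Reproduce SAP Table 4.** Its follow-up targets for Part C completers are days 365, 393, 421 and 477.
- Last dose on day 309: 309 + 56, + 84, + 112, + 168 = 365, 393, 421, 477. All match.
- Last dose on day 337: 393, 421, 449, 505. The targets do not match.

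Table 4 and the completion rule in SAP 4.5 (at least 44 weeks of dosing plus a week 48 visit) therefore imply a last dose at week 44. The Part C schedule of events, in both documents, marks dosing at week 48. I carry both.

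**2. Unobserved time in Part C** for a patient last seen at EOT (day 337):

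| Last dose | TEAE period ends | Unobserved | Share of Part C period |
|---|---|---|---|
| Week 44 | 309 + 168 = 477 | 477 − 337 = 140 days (20 weeks) | 140/477 = 29% |
| Week 48 | 337 + 168 = 505 | 505 − 337 = 168 days (24 weeks) | 168/505 = 33% |

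**3. Pooled Parts B and C, Part B patient.** If Part C day 1 falls on Part B day 169, add 168 days. EOT is day 337 + 168 = 505. The period ends on day 477 + 168 = 645 or 505 + 168 = 673. The shares are 140/645 = 22% and 168/673 = 25%.

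**4. Effect on a Part C curve (illustration).** Assume that all 20 patients enter Part C, m leave at EOT, and one followed patient has a first event after EOT while the leavers are still in the risk set, with no other events or censoring. The SAP rule gives a drop of 1/20 = 5%. Censoring at last contact gives 1/(20 − m): 6.7% for m = 5, 10% for m = 10, 20% for m = 15. The documents give no uptake figure, so m is assumed.

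**5. Effect on the pooled Total column (illustration).** Part A patients enter the pool at Part C day 1 (SAP 2.4.1), so their EOT is about pooled day 337, against about day 505 for Part B patients. Suppose that all 6 Part A patients leave at EOT and one Part B patient has a first event after day 337, before the Part A patients' TEAE periods end (day 477 or 505). With all 20 in Part C and otherwise event-free, the SAP rule gives 1/20 = 5%; censoring at last contact gives 1/14 = 7.1%. Here the event falls while Part B patients are still on treatment and under observation, so no post-treatment event is needed.

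**6. Disposition.** EOT minus last dose is 337 − 309 = 28 days or 337 − 337 = 0 days. Both are below 154, so every patient who exits at EOT is counted as not completing follow-up.

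**The case against.** Much can be said against a broad version of this point, and most of it stands.

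- A reader might infer that adverse event results in general are biased. They are not. The planned tables are counts and percentages over the safety analysis set (SAP 5.8.1), infusion reactions are related to the number of administrations (SAP 5.8.2), and no exposure-adjusted event rate is planned. The curves are optional and depend on a signal.
- A reader might infer that every Kaplan-Meier estimate is too low. For Part C treatment completers, risk sets before EOT do not change, so the Part C curve moves only if a followed patient has a first event after EOT. If nearly everyone leaves at EOT, such an event is unlikely to be seen and the main change is a longer flat tail. The pooled Total column remains exposed, as step 5 shows.
- A reader might infer that the TEAE period always runs to 168 days. The truncations at Part C entry and at the interim cut-offs show otherwise.
- A reader might extend the problem to anyone who stops drug early. The protocol asks such patients to keep attending (8.4.2), or otherwise to be followed for at least 24 weeks (9.1.2). The gap is limited to consent withdrawal and actual loss to follow-up.
- Data after EOT are not wholly absent. Several passages say that patients may, not must, forgo follow-up, and related serious events arising after the reporting period are still reportable (protocol 10.1.1).
- The SAP's disposition label is literally true of these patients. A reader might see widespread loss to follow-up, or all 20 patients misreported, but the documents give no uptake figure to support either.

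The SAP also provides for revision after protocol amendments (Section 1). That explains the gap; it does not close it in the text available.

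**Conclusion.** The point holds in a limited form. In the final Part C and pooled analyses, the stated rule keeps event-free patients who leave at EOT for a CUP or EAP in the risk set for 140 to 168 unobserved days. Which end of that range applies depends on the week 44 versus week 48 conflict, but the conclusion is the same at both ends. Where curves are produced, incidence after EOT can be understated. The size depends on uptake and on a late event occurring; the percentages in steps 4 and 5 are illustrations under stated assumptions, not forecasts.

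The disposition problem does not depend on a signal, because that table is planned in any case (SAP 5.5). Its consequence is loss of information about why follow-up ended, not a wrong count under the SAP's own definition.

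**What to change.** - **SAP 5.8.1, all three places:** censor event-free patients at the earlier of the end of the TEAE period and the last study contact. This also covers consent withdrawal and loss to follow-up.
- **SAP 4.8.1:** leave the TEAE period as defined. Ending it at last contact is not needed for the curves and could move later-reported related serious events out of the TEAE tables.
- **SAP 4.5:** add a separate category for patients who entered a CUP or EAP and for whom follow-up was not required, and take them out of the non-completer count.
- **Last Part C dose:** reconcile SAP Table 4 and the completion rule with the Part C schedule of events.

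The cost is SAP wording and a data flag for CUP/EAP entry. No visit, dose or treatment rule needs to change for the censoring and disposition edits.

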5.8.2. Analysis of Adverse Events of Special Interest

Treatment-emergent adverse events of special interest (AESI), as listed in Section 4.8.1.2, will be presented by SOC and PT as applicable. AESI are defined by SMQ, CMQ, lab data, and/or dedicated e-CRF as described in [Appendix 10.3](#).

The following variables will also be tabulated for infusion reactions TEAEs:

- Intensity of the event (mild, moderate, or severe);
- Number of events divided by the number of study treatment administrations received in respective treatment periods;
- Time from first study treatment administration to first infusion reaction;

5.8.3. Clinical Laboratory Measurements

The following definitions will be applied to laboratory parameters:

- Part A treatment and observation period: the period used for quantitative analysis for Part A is defined from the day after the first study treatment administration to the day of last visit during the Part A observation period.
- Part B treatment period: the treatment period used for quantitative analysis is defined from the day after the first study treatment administration to the day of the last study treatment administration + 28 days for those patients not proceeding into Part C, or up to the day of the first study treatment administration in Part C for those patients proceeding into Part C.
- Part C treatment period: the treatment period used for quantitative analysis is defined from the day after the first study treatment administration in Part C to the day of the last study treatment administration in Part C + 28 days.
- Pooled treatment period: for Part A patients, the treatment period used for quantitative analysis is defined from the day after the first study treatment administration in Part C to the day of the last study treatment administration in Part C + 28 days. For Part B patients, the treatment period used for quantitative analysis is

defined from the day after the first study treatment administration in Part B to the day of the last study treatment administration in Part C + 28 days or to last study treatment administration in Part B + 28 days for patients not entering into the Part C.

For respective treatment period, clinical laboratory parameter actual values (quantitative) and change from baseline values will be descriptively summarized at baseline and each post-baseline visit by at least patient number, mean, median, Q1, Q3, SD, minimum and maximum. Clinical laboratory parameters mean changes from baseline, with the corresponding SE, can be plotted at each visit in the case results warrant further investigation. These parameters will be presented by the biological functions defined in Section 4.8.2. For glucose, only fasting samples will be included in the summaries.

Individual patient laboratory parameter measurements will be additionally evaluated by PCSV criteria (See Appendix 10.4), specifically identifying patients with at least one post-baseline measurement that meets the PCSV criteria within the respective TEAE periods. These laboratory parameters will be presented by the biological functions defined in Section 4.8.2. The incidence of PCSVs at any time during the respective TEAE periods will be summarized regardless of the baseline level, and again according to the following baseline categories:

- Normal (according to PCSV criterion/criteria)/missing
- Abnormal according to PCSV criterion or criteria

Patient listings of laboratory measurements that meet PCSV criteria will be provided for the report appendix. For those laboratory parameters that don't have an associated PCSV criteria, similar summary tables can be provided based on measurements outside the central laboratory normal ranges, if applicable.

Drug-induced liver injury

For respective treatment period, an evaluation of drug-induced serious hepatotoxicity (eDISH) with the graph of distribution of peak values of ALT versus peak values of total bilirubin will also be presented using post-baseline values during respective TEAE periods. Note that the ALT and total bilirubin values are presented on a logarithmic scale. The graph will be divided into 4 quadrants with a vertical line corresponding to 3 x ULN for ALT and a horizontal line corresponding to 2 x ULN for total bilirubin.

Patient listing of possible Hy's law cases identified (i.e., patients with any elevated ALT > 3 x ULN, and associated with an increase in bilirubin > 2 x ULN, concomitantly or not) with ALT, AST, ALP, total bilirubin, and if available direct and indirect bilirubin will be provided.

Sex hormones

For respective treatment period, the sex hormones will be described separately by gender.

- For girls
 - Values and changes from baseline will be descriptively summarized by time point for estradiol, FSH and LH.
 - Similar table as for PCSA will be provided using normal range during the respective TEAE period. The number (%) of patients with at least one estradiol

value <LLN and LH >ULN, estradiol value<LLN and FSH >ULN, estradiol value <LLN and LH>ULN and FSH >ULN) during the TEAE period.

- For boys
 - Values and changes from baseline will be descriptively summarized by time point for testosterone, FSH and LH.
 - Similar table as for PCSA will be provided using the normal range. The number (%) of patients with at least one testosterone value <LLN and LH >ULN, testosterone value<LLN and FSH >ULN, testosterone value<LLN and LH>ULN and FSH >ULN) during the respective TEAE period.

5.8.4. Analysis of Vital Signs

For respective treatment period as defined for clinical laboratory measurements (Section 4.8.2), the vital sign actual values and change from baseline values obtained while sitting will be descriptively summarized at baseline and each post-baseline visit by at least patient number, mean, median, Q1, Q3, SD, minimum and maximum. Mean changes from baseline, with the corresponding SE, can be plotted at each visit in the case results warrant further investigation.

Individual patient vital sign measurements (regardless of sitting position) will be additionally evaluated by PCSV criteria, specifically identifying patients with at least one post-baseline measurement that meets the PCSV criteria within the TEAE period. The incidence of PCSVs at any time during the respective TEAE periods will be summarized regardless of the baseline level, and again according to the following baseline categories:

- Normal (according to PCSV criterion/criteria)/missing
- Abnormal according to PCSV criterion or criteria

Patient listings of vital sign measurements that meet PCSV criteria will be provided for the report appendix.

